**Table 6-8 Efficacy Analysis Visit Definitions for MSQ v2.1, PGIC, and MIDAS**

Analysis Phase	Analysis Visit (Derived)	Scheduled Study Visit (eCRF)	Window
Pretreatment*	Baseline	Visit 1 for De Novo EM Participant only	Baseline from lead-in study for 3101-303-002 Completer Treatment Day $\leq$ 1 for De Novo EM Participant
Open-label Treatment Period	Week 12	Visit 4	Treatment Day [1, 126] for 3101-303-002 Completer Treatment Day [2, 126] for De Novo EM Participant
	Week 24	Visit 7	Treatment Day [127, 210]
	Week 36	Visit 10	Treatment Day [211, 294]
	Week 48	Visit 13	Treatment Day [295, 350]
	Week 52	Visit 14/ET	Treatment Day $\geq$ 351 and within open-label treatment period
Safety Follow-up Period**	Week 56 (Follow-up)	Visit 15	Treatment Day [the end of open-label treatment period +1, the last study visit]

ET early termination

\* Only for MSQ v2.1 and MIDAS.

\*\* Only for MSQ v2.1.

The analysis visit windows for HIT-6, EQ-5D-5L, PGI-S, Patient Satisfaction with Study Medication, and WPAI:MIGRAINE are defined as follows:

**Table 6-9 Efficacy Analysis Visit Definitions for HIT-6, EQ-5D-5L, PGI-S, Patient Satisfaction with Study Medication, and WPAI:MIGRAINE**

Analysis Phase	Analysis Visit (Derived)	Scheduled Study Visit (eCRF)	Window
Pretreatment*	Baseline	Visit 1 for De Novo EM Participant only	Baseline from lead-in study for 3101-303-002 Completer Treatment Day $\leq$ 1 for De Novo EM Participant
Open-label Treatment Period	Week 4	Visit 2	Treatment Day [1, 42] for 3101-303-002 Completer Treatment Day [2, 42] for De Novo EM Participant
	Week 8	Visit 3	Treatment Day [43, 70]
	Week 12	Visit 4	Treatment Day [71, 98]
	Week 16	Visit 5	Treatment Day [99, 126]
	Week 20	Visit 6	Treatment Day [127, 154]
	Week 24	Visit 7	Treatment Day [155, 182]
	Week 28	Visit 8	Treatment Day [183, 210]
	Week 32	Visit 9	Treatment Day [211, 238]
	Week 36	Visit 10	Treatment Day [239, 266]
	Week 40	Visit 11	Treatment Day [267, 294]
	Week 44	Visit 12	Treatment Day [295, 322]
	Week 48	Visit 13	Treatment Day [323, 350]
	Week 52	Visit 14/ET	Treatment Day $\geq$ 351 and within open-label treatment period
Safety Follow-up Period**	Week 56 (Follow-up)	Visit 15	Treatment Day [the end of open-label treatment period +1, the last study visit]

ET = early termination

\* Only for HIT 6, EQ 5D 5L and PGI S.

\*\* Only for HIT 6 and EQ 5D 5L.

The analysis visit windows for safety endpoints are defined as follows:

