8.4.2.3 Visit 14/Early Termination (Week 52)

Effort should be made by the site to not schedule Visit 14 earlier than 52 weeks after Day 1, to ensure participants complete the full 52 weeks of atogepant and have eDiary data through Day 364.

- Prior to any other test or evaluations, administer the following PRO measures: HIT-6, PGIC, PGI-S, WPAI:MIGRAINE, Patient Satisfaction with Study Medication, EQ-5D-5L, MIDAS, and MSQ v2.1.
- Perform physical examination.
- Perform urine pregnancy test for women of childbearing potential.
- Collect vital sign measurements (sitting and standing systolic and diastolic BP, sitting and standing pulse rate, respiration rate, temperature, and weight).
- Collect blood and urine samples for chemistry, hematology, INR, and urinalysis.
- Assess C-SSRS (the “Since Last Visit” assessment of the C-SSRS will be completed).
- Perform and transmit ECG.
- Review and assess AEs.
- Review and update concomitant medications and concurrent procedures.
- Review eDiary data and compliance.
- Collect eDiary.
- Collect previous visit atogepant bottle, review participant compliance and perform accountability.
- Access IWRS to enter study visit and accountability.

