8.8 Early Discontinuation of Participants

A premature discontinuation will occur when a participant who signed the ICF ceases participation in the study, regardless of circumstances, before completion of the study. Participants can be prematurely discontinued from the study for one of the following reasons:

- AE
- Lack of efficacy
- Lost to follow-up
- Noncompliance with study intervention (ie, atogepant)

- Pregnancy
- Protocol deviation
- Site terminated by Sponsor
- Study terminated by Sponsor
- Withdrawal by participant

Participants may voluntarily withdraw from the study at any time.

Notification of early participant discontinuation from the study and the reason for discontinuation will be made to the sponsor and will be clearly documented on the appropriate eCRF. All participants who prematurely discontinue from the study, regardless of cause, should be seen for final study assessments. The final assessments will be defined as completion of the evaluations scheduled for Visit 14/ET and Visit 15/EOS; 4 weeks after the last dose of atogepant.

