##### **5.3.4.2. Migraine Disability Assessment (MIDAS)**

The MIDAS is a 7-item questionnaire designed to quantify headache-related disability over a 3-month period. The MIDAS score is the sum of missed work or school days, missed household work days, days at work or school plus days of household work where productivity was reduced by half or more, and missed non-work activity days due to headaches in the last 3 months.

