**Table 6-10 Safety Analysis Visit Definitions**

Analysis Phase	Analysis Visit (Derived)	Scheduled Study Visit (eCRF)	Window
Pretreatment	Baseline	Visit 1 for De Novo EM Participant only	Baseline from lead-in study for 3101-303-002 Completer Treatment Day $\leq 1$ for De Novo EM Participant
Open-label Treatment Period	Week 4	Visit 2	Treatment Day [1, 42] for 3101-303-002 Completer Treatment Day [2, 42] for De Novo EM Participant
	Week 8	Visit 3	Treatment Day [43,70]
	Week 12	Visit 4	Treatment Day [71,98]
	Week 16	Visit 5	Treatment Day [99,126]
	Week 20	Visit 6	Treatment Day [127,154]
	Week 24	Visit 7	Treatment Day [155,182]
	Week 28	Visit 8	Treatment Day [183,210]
	Week 32	Visit 9	Treatment Day [211,238]
	Week 36	Visit 10	Treatment Day [239,266]
	Week 40	Visit 11	Treatment Day [267,294]
	Week 44	Visit 12	Treatment Day [295,322]
	Week 48	Visit 13	Treatment Day [323,350]
	Week 52	Visit 14/ET	Treatment Day $\geq 351$ and within open-label treatment period
	End of treatment		Last available assessment during open-label treatment period
Safety Follow-up Period	Week 56 (Safety follow-up)	Visit 15	Treatment Day [the end of open-label treatment period +1, the last study visit]
	End of study		Last available assessment after treatment start date, i.e., occurs at final visit (expected Day 392) or ET

ET = early termination

Safety follow up visit will be presented in analysis tables for clinical laboratory values and vital signs.

End of Open label Treatment is defined as the last available assessment during open label treatment period. End of Open label Treatment results will be presented in analysis tables for clinical laboratory values, electrocardiograms and vital signs.

End of Study is defined as the last available assessment during the study, including open label and safety follow up period. End of Study results will be presented in analysis tables for safety parameters, including but not limited to clinical laboratory values, and vital signs.

For endpoints collected by visit, the last visit with a non-missing value will be used for analysis, if a participant has 2 or more visits within the same window.

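### The Week 12 window for MSQ v2.1, MIDAS and PGIC opens at Day 1 or 2, so some Visit 1 scores and early-termination scores can be analysed as Week 12 results

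*SAP*

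**What the plan says.** SAP Table 6-8 gives the Week 12 window as "Treatment Day [1, 126] for 3101-303-002 Completer" and "Treatment Day [2, 126] for De Novo EM Participant". The Week 24 window begins and ends at "Treatment Day [127, 210". The only row tied to Visit 14/ET is Week 52, which requires Day "351 and within open-label treatment period" or later, so an earlier termination visit cannot map there.

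All three instruments are given at the termination visit. Protocol 8.4.2.3 tells sites to "administer the following PRO measures: HIT-6, PGIC, PGI-S, WPAI:MIGRAINE, Patient Satisfaction with Study Medication, EQ-5D-5L, MIDAS, and MSQ v2.1", and Protocol 8.8 states: "All participants who prematurely discontinue from the study, regardless of cause, should be seen for final study assessments". Where several values share a window, the SAP note after Table 6-10 says that "the last visit with a non-missing value will be used for analysis, if a participant has 2 or more visits within the same window".

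MSQ and MIDAS, but not PGIC, are also given at Visit 1, before drug is dispensed (Protocol 8.4.2.1). Completers take their baseline from the lead-in study (SAP 5.1), so their Visit 1 scores are not baseline values here. MIDAS is "designed to quantify headache-related disability over a 3-month period" (SAP 5.3.4.2), and MSQ has a 4-week recall (SAP 6.4.3).

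**The concern.** A window should collect values nearer to its own target than to another scheduled assessment. The first third of this one lies nearer to Day 1 than to Visit 4. A score taken then, under a 3-month or 4-week recall, partly or wholly describes time before open-label treatment, yet it would be averaged with scores taken after 12 weeks on drug.

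The labelling is also inconsistent within a participant. A termination visit on Day 20 counts as Week 4 for HIT-6 under SAP Table 6-9 and as Week 12 for MSQ, MIDAS and PGIC under Table 6-8.

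What is at stake is the meaning of the Week 12 summaries for these instruments. It also touches the MSQ Role Function-Restrictive estimate and 95% CI, which come from a mixed model for repeated measures (SAP 5.3.1) in which Week 12 is the first post-baseline visit.

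**Working it through.** **Reproducing the table.** The scheduled days are 84, 168, 252, 336 and 364 (Protocol Table 1). The midpoints are:
- (84 + 168)/2 = 126
- (168 + 252)/2 = 210
- (252 + 336)/2 = 294
- (336 + 364)/2 = 350

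All four upper bounds match. The Week 12 lower bound does not follow the rule; it is the first day after the baseline window.

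**Asymmetry.** Week 12 reaches 84 − 1 = 83 days (Completers) or 84 − 2 = 82 days (De Novo EM) before target, and 126 − 84 = 42 days after. Week 24 reaches 168 − 127 = 41 before and 210 − 168 = 42 after. The midpoint of Days 1 and 84 is 42.5, which gives Days 43 to 126. That window is 84 days wide, the same as Week 24. Days below 43 make up 42/126 = 33% of the Completer window and 41/125 = 33% of the De Novo window.

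**Route 1: Visit 1 scores of Completers.** Day 1 is the date of first open-label dose (SAP 6.4). If that is the Visit 1 date, the pre-dose MSQ and MIDAS fall in the Week 12 window. Any later value by Day 126 replaces them; if there is none, they stand as Week 12. This does not require dropout. A continuing participant can miss the Visit 4 questionnaires, because at remote visits the web portal is used only if available (Protocol 8.4.4). The documents give no basis for a count.

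**Route 2: early-termination visits.** Efficacy uses the mITT set, which needs one evaluable 4-week eDiary period (SAP 4), meaning at least 14 diary days (SAP 6.4.2.1). The eDiary is collected at the termination visit, so the earliest such visit that can contribute is about Day 14 to 15.

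Share of recall before Day 1, for a visit on Day d:
- MIDAS, taking 3 months as 84 days: (84 − d)/84. Day 15: 69/84 = 82%. Day 28: 56/84 = 67%. Day 42: 42/84 = 50%.
- MSQ: (28 − d)/28. Day 15: 13/28 = 46%. Day 20: 8/28 = 29%. Day 28 onward: 0%.
- PGIC asks about change since first dose, so it has no pre-treatment recall; only its label is affected.

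**How many by Route 2.** The plan states no dropout rate. I assume N = 170, a constant hazard and 52-week retention r from 100/170 = 59% to 90%. With S(d) = r^(d/364), the number stopping on Days 15 to 42 is 170 × [S(14) − S(42)].
- r = 0.588: 170 × (0.980 − 0.941), about 6.7, or 4.0% of those still in at Day 14
- r = 0.90: 170 × (0.996 − 0.988), about 1.4, or 0.8% of those still in at Day 14

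A further 0.7 to 3.4 stop by Day 14 and are largely kept out by the mITT rule. These counts assume that every leaver completes the questionnaires.

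**An open boundary.** Route 2 requires the visit to fall within the open-label treatment period. The SAP uses the end of that period as a boundary but does not define it; the note under Table 6-10 defines only the last assessment inside it. If the period ends at the termination visit, Route 2 applies. If it ends at the last dose, a later termination visit sends MSQ to Week 56 and leaves MIDAS and PGIC with no window.

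**The case against.** The strongest defence is that opening the first post-baseline window straight after baseline is the SAP's convention in Tables 6-8, 6-9 and 6-10, so the bound is a choice and not a contradiction. That stands. But in Tables 6-9 and 6-10 the first scheduled visit is Day 28 and in Table 6-8 it is Day 84, so the same convention admits far earlier values here.

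It can also be said that dropping early values removes observed outcomes of people who left, and makes the Week 12 group more selected. That is a fair cost, but small at the counts above.

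Several stronger readings are tempting and are not supported:
- *Visits within days of starting treatment enter as Week 12.* A termination visit on Day 10 cannot supply 14 diary days, so that participant is outside mITT.
- *About 10 participants are affected.* 170 × (1 − 0.588^(42/364)) = 10 counts everyone leaving by Day 42, including those whom mITT excludes. It also treats 1 − 100/170 = 41% as planned attrition, whereas 170 and 100 are both minimum figures set by regulatory exposure requirements (SAP 3).
- *The Week 12 MSQ score mostly describes time before treatment.* For termination visits the share is about 46% at Day 15 and nil by Day 28. Only MIDAS is affected to that degree.
- *Time before Day 1 is untreated.* For Completers it need not be, since the lead-in arms included atogepant (SAP 5.2).

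**Conclusion.** The point holds as a minor defect in Table 6-8. The rule as written can label a pre-dose Day 1 score (Completers) or a termination score from about Day 14 to 15 as Week 12. The first route depends on dosing starting on the Visit 1 date and on no later value by Day 126. The second depends on how the end of the open-label period is read.

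The second route involves about 1 to 7 of 170 participants on Days 15 to 42, under assumed retention and constant hazard. The first cannot be sized from the documents. Interpretation of the Week 12 patient-reported results is affected, most of all MIDAS, along with the MSQ Role Function-Restrictive model estimate. The study has no statistical hypothesis and efficacy is secondary to safety, so no test and no safety conclusion changes.

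**What to change.** - In Table 6-8, set the Week 12 window to Treatment Day 43 to 126 for both cohorts.
- Report MSQ, MIDAS and PGIC values from earlier termination visits in a separate row, and state that they do not enter the Week 12 summary or the MSQ model.
- State that Completers' Visit 1 scores are not used as Week 12 values.
- Define the end of the open-label treatment period, so that termination visits map the same way for every instrument.

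The cost is one table edit, one definition and one extra summary row. A few early observed values leave the Week 12 summary and the MSQ model. The change is not a complete cure for MIDAS: at Day 43 about 41/84 = 49% of its recall still precedes Day 1, and a footnote should say so.

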**Table 6-10 Safety Analysis Visit Definitions**

Analysis Phase	Analysis Visit (Derived)	Scheduled Study Visit (eCRF)	Window
Pretreatment	Baseline	Visit 1 for De Novo EM Participant only	Baseline from lead-in study for 3101-303-002 Completer Treatment Day $\leq 1$ for De Novo EM Participant
Open-label Treatment Period	Week 4	Visit 2	Treatment Day [1, 42] for 3101-303-002 Completer Treatment Day [2, 42] for De Novo EM Participant
	Week 8	Visit 3	Treatment Day [43,70]
	Week 12	Visit 4	Treatment Day [71,98]
	Week 16	Visit 5	Treatment Day [99,126]
	Week 20	Visit 6	Treatment Day [127,154]
	Week 24	Visit 7	Treatment Day [155,182]
	Week 28	Visit 8	Treatment Day [183,210]
	Week 32	Visit 9	Treatment Day [211,238]
	Week 36	Visit 10	Treatment Day [239,266]
	Week 40	Visit 11	Treatment Day [267,294]
	Week 44	Visit 12	Treatment Day [295,322]
	Week 48	Visit 13	Treatment Day [323,350]
	Week 52	Visit 14/ET	Treatment Day $\geq 351$ and within open-label treatment period
	End of treatment		Last available assessment during open-label treatment period
Safety Follow-up Period	Week 56 (Safety follow-up)	Visit 15	Treatment Day [the end of open-label treatment period +1, the last study visit]
	End of study		Last available assessment after treatment start date, i.e., occurs at final visit (expected Day 392) or ET

ET = early termination

Safety follow up visit will be presented in analysis tables for clinical laboratory values and vital signs.

End of Open label Treatment is defined as the last available assessment during open label treatment period. End of Open label Treatment results will be presented in analysis tables for clinical laboratory values, electrocardiograms and vital signs.

End of Study is defined as the last available assessment during the study, including open label and safety follow up period. End of Study results will be presented in analysis tables for safety parameters, including but not limited to clinical laboratory values, and vital signs.

For endpoints collected by visit, the last visit with a non-missing value will be used for analysis, if a participant has 2 or more visits within the same window.

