## 5. Statistical Analyses

### 5.1. General Considerations

- Efficacy endpoints will be analyzed descriptively based on the mITT population.
- Safety endpoints will be performed using the Safety population.
- Continuous variables will be summarized by number of participants with observed values (n), mean, standard deviation (SD), median, 1st and 3rd quartiles (Q1, Q3), minimum (min), and maximum (max).
- Categorical variables will be summarized by number of participants with observed values, events (n), frequency count (n1), and percentage of participants with observed values.
- Partial dates will be treated as missing in computation or in variable derivation unless specified otherwise, but will be listed in the data listings as they appear on the eCRF.
- For monthly endpoints, baseline is defined as assessments during the last 28 days of baseline period in the lead-in study for 3101-303-002 rollover participants, and the last 28 days of the screening/baseline period for De Novo EM Participants. For efficacy endpoints that are assessed at clinical visits, baseline is defined as the last non-missing efficacy assessment before the first dose of study intervention in the lead-in study (3101-303-002) for 3101-303-002 Completers, and the last non-missing efficacy assessment before the first dose of study for De Novo EM Participants. For each of the clinical, laboratory, vital sign, and ECG parameters, the baseline is defined as the baseline value in the lead-in study (3101-303-002) for 3101-303-002 Completers, and the last nonmissing safety assessment before the first dose of study drug for De Novo EM Participants.
- The change from baseline values will be computed as the post-baseline value minus the baseline value.
- Study intervention is treatment administered (atogepant 60 mg QD).
- All statistical analysis will be performed using SAS version 9.4 or higher.
- Medical Dictionary for Regulatory Activities (MedDRA), Version 27.0 or higher, will be used to code adverse events and medical history.
- WHO Drug Global B3 (v.202403 or higher) will be used to code medications.

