#### **5.4.4.3. Electrocardiogram**

Descriptive statistics for ECG parameters (i.e., heart rate, PR interval, QRS interval, RR interval, QT interval, and QTc interval) and changes from baseline values at each assessment timepoint will be presented. The QTc will be calculated using the Fridericia correction.

ECG parameter values are considered PCS if ECG values meet either the actual value or change from baseline PCS high criteria listed in [Table 6-5](#). The number and percentage of participants with PCS postbaseline values will be tabulated. The percentages will be calculated relative to the number of participants with an available non-PCS baseline value and at least 1 postbaseline assessment. The numerator will be the total number of participants with an available non-PCS baseline value and at least 1 PCS postbaseline ECG value during the study. A supportive listing of participants with PCS postbaseline values will be provided. A listing of all AEs for participants with PCS ECG values will also be provided.

To evaluate ECG postbaseline values of clinical interest, the number and percentage of participants with post-treatment QTcF  $> 450$  msec,  $> 480$  msec, and  $> 500$  msec will be tabulated. A supportive listing of participants with postbaseline clinical interest will be provided. A listing of all AEs for participants with postbaseline clinical interest will also be provided.

The number and percentage of participants with an increase  $> 30$  msec but  $\leq 60$  msec, and with an increase  $> 60$  msec in QTcF will be tabulated. Participants will be counted only once for the most severe category. A supportive listing of participants with postbaseline QTcF increases  $> 30$  msec will be provided, including the PID number and all QTc values (including changes from baseline). A listing of all AEs for participants with postbaseline QTcF increases  $> 30$  msec will also be provided.

A shift table from baseline to the end of open-label treatment period in the investigator's overall interpretation of the ECG will be presented for the following categories: normal; abnormal, not clinically significant; abnormal, clinically significant. A tabular display of participants with postbaseline clinically significant ECG abnormalities according to the investigator's overall interpretation will be provided.

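### SAP Table 6-10 counts a Completer's pre-dose Visit 1 assessments as open-label 'Week 4', so a pre-dose ECG or liver value can be reported as on-treatment safety data

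*SAP*

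**What the plan says.** SAP 6.4 makes Treatment Day 1 the date of the first open-label dose, with no Day 0. SAP Table 6-10 then gives the Week 4 safety window as "Treatment Day [1, 42] for 3101-303-002 Completer Treatment Day [2, 42] for De Novo EM Participant". The same table names Visit 1 as the baseline visit for De Novo EM participants only. For Completers, SAP 5.1 states that "the baseline is defined as the baseline value in the lead-in study (3101-303-002) for 3101-303-002 Completers".

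Where a window holds several visits, "the last visit with a non-missing value will be used for analysis". For the end-of-treatment row, "End of Open label Treatment is defined as the last available assessment during open label treatment period", and "End of Open label Treatment results will be presented in analysis tables for clinical laboratory values, electrocardiograms and vital signs". The end-of-study row of the same table is worded differently: "Last available assessment after treatment start date".

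SAP 5.4.4.3 plans "A shift table from baseline to the end of open-label treatment period" for the investigator's ECG interpretation. It also plans to tabulate "the number and percentage of participants with post-treatment QTcF" above fixed limits, without defining post-treatment. SAP 5.4.4.1 counts a participant in a row of hepatic Table 6-4 on any postbaseline value that meets it, with no condition on the baseline value. SAP 6.4.4 uses every postbaseline assessment for PCS (potentially clinically significant) determinations. It also defines baseline by the first dose of study treatment without saying which study's treatment is meant.

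Protocol 8.4.2.1 lists the Visit 1 ECG (Completers only) and blood sampling ahead of dispensing, which is the last step. Protocol 8.9 requires withdrawal of Completers whose Visit 1 ALT, AST or total bilirubin exceeds 1 x ULN (Gilbert's disease excepted for bilirubin).

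**The concern.** The two cohorts have the same sequence at Visit 1: assessment first, drug afterwards. Table 6-10 treats a Day 1 value as pretreatment in one cohort and as open-label in the other. Two problems follow, with different causes.

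- **Window.** A pre-dose ECG can fill the Week 4 row and can stand as the end-of-treatment result.
- **Meaning of postbaseline.** Because the Completer baseline is the lead-in value, everything at Visit 1 is postbaseline whatever window it falls in. An abnormality found at entry to the extension is then counted as arising during it.

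Safety over 52 weeks is the primary objective, and SAP 5.5.1 presents all safety endpoints by cohort. For direct rollovers from the lead-in atogepant arms, Visit 1 does reflect atogepant exposure. It does not for lead-in placebo participants, one of the three lead-in treatments in SAP 5.2. Nor does it for those who entered at or after lead-in Visit 8, because Protocol 3.1 has them stop study intervention first.

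The error does not run in one direction. It adds pre-dose liver elevations, but it also lets a pre-dose ECG take the place of a missing on-treatment one, and lets an unassessed participant meet the postbaseline-assessment requirement of the denominators.

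**Working it through.** There is no planned figure to reproduce; the check maps scheduled visits onto the Table 6-10 windows. It assumes that the first open-label dose is taken on the Visit 1 date. If it is taken the next day, Visit 1 is Day -1 and falls in no Completer window.

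**ECG.** Days are from Protocol 8.4.2.1 to 8.4.2.3 and Table 1, with the visit tolerances applied.

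| Visit | Day range | Window as written | Window if the lower bound is Day 2 |
|---|---|---|---|
| 1 | 1 (pre-dose) | Week 4 | pretreatment |
| 4 | 81–87 | Week 12 | Week 12 |
| 7 | 165–171 | Week 24 | Week 24 |
| 10 | 249–255 | Week 36 | Week 36 |
| 14 | 364–367 | Week 52 | Week 52 |

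- Scheduled ECGs on Days 2–42: 0.
- Earliest scheduled ECG after Visit 1: 84 − 3 = Day 81, which is 81 − 42 = 39 days after the Week 4 window closes.
- An early-termination ECG on Days 2–42 would also map to Week 4 and replace Visit 1. A Completer who leaves before Week 12 with no such tracing and no unscheduled one has Visit 1 as the last open-label ECG, hence as the end-of-treatment value and the endpoint of the shift table.

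**Laboratory.**

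- Visit 2: 28 ± 3 = Days 25–31, inside [1, 42]. It replaces Visit 1 under the last-visit rule.
- If Visit 2 is missed, or is remote (Protocol Table 2 has no laboratory row), the next scheduled sample is Visit 3: 56 ± 3 = Days 53–59, inside [43, 70]. That is at least 53 − 42 = 11 days too late to replace Visit 1, which then stands as Week 4.

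**Hepatic table.**

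1. A Visit 1 value above 1 x ULN necessarily meets the ≥ 1 x ULN criterion.
2. Drug is dispensed at that visit and samples go to a central laboratory (Protocol 6.1.3), so a result can arrive after dosing. This is an inference; the documents do not give the timing.
3. Anyone dosed is in the Safety population (SAP section 4), and under SAP 5.1 the Visit 1 value is postbaseline.
4. The participant therefore enters the ≥ 1 x ULN row, the lowest of 7 thresholds per analyte. Higher rows and PCS are reached only if the value is high enough. The albumin criterion in Protocol 8.9 has no row in Table 6-4.

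The weight per affected Completer, at the planned minimum sizes, is 1/140 = 0.71 percentage points in the Completer column and 1/170 = 0.59 overall. The number affected, k, is not given. Purely as a range:

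| k (assumed) | k/140 | k/170 |
|---|---|---|
| 1 | 0.71% | 0.59% |
| 3 | 2.14% | 1.76% |
| 5 | 3.57% | 2.94% |

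Moving the window to Day 2 repairs the ECG problem and leaves the usual Week 4 laboratory value unchanged. It does not repair the hepatic row, because that count depends on the baseline and not on the window.

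**The case against.** The lead-in baseline is deliberate. The SAP version history records the change as alignment with other atogepant extension studies, and the Day 1 start for Completers recurs in Tables 6-8 and 6-9, so this is a convention and not a slip. ECG summaries are promised at assessment timepoints and no Week 4 ECG is planned, so that row might never be printed; the table shells are in a separate document. The end-of-treatment effect needs early departure without an early-termination ECG, although Protocol 8.8 and 8.9 ask for final assessments in everyone who leaves. The hepatic effect is certain only in the lowest row, overstates rather than hides a liver signal, and leaves the ≥ 3 x ULN special-interest threshold and the Hy's law summary largely untouched. A participant still elevated at early termination would be counted in any case.

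Most of this stands as a limit on size. The lead-in baseline is a legitimate choice for change scores, the end-of-treatment case should be uncommon, and no count can be attached to the hepatic case. None of it justifies labelling a pre-dose assessment as open-label. The same lower bound in the other tables widens the issue rather than curing it. The SAP already starts both the TEAE definition (5.4.3) and the Hy's law summary (5.4.4.1) at first dose, so the window and hepatic rules are out of step with their neighbours.

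**Conclusion.** The concern holds. As written, Table 6-10 places pre-dose Visit 1 data of Completers dosed that day in the open-label period. Visit 1 is the only calendar-scheduled source of a Completer Week 4 ECG and can become the end-of-treatment ECG. Independently, under the lead-in baseline, a dosed Completer withdrawn for a Visit 1 liver value is counted in the ≥ 1 x ULN row on a pre-dose sample, at 0.71 percentage points of the Completer column each.

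Three points of reading matter. The hepatic conclusion takes SAP 5.1 and Table 6-10 as governing; SAP 6.4.4, if it means the open-label dose, contradicts them. The QTcF categories include Visit 1 only if the undefined term post-treatment is read as postbaseline. Pre-dose here means before extension dosing, and some Completers were already on atogepant. The defect should be corrected, but nothing in the documents shows that it would change a safety conclusion.

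**What to change.** - **SAP Table 6-10:** start the Completer Week 4 window at Treatment Day 2. Add a pretreatment visit for Completers, 'Extension entry (Visit 1)', shown as its own line by lead-in arm, with Protocol 8.9 Visit 1 withdrawals listed there by criterion. Define 'End of treatment' as the last assessment after the first open-label dose and within the open-label period. Review the same Day 1 bound in Tables 6-8 and 6-9.
- **SAP 5.4.4.1 to 5.4.4.3:** define 'postbaseline' and 'post-treatment' as after the first open-label dose (Treatment Day 2 or later if no dose time is recorded). Apply this to Table 6-4, PCS, the QTcF categories and the denominator condition. Keep the lead-in baseline for change scores.
- **SAP 6.4.4:** replace the baseline sentence with a reference to 5.1.

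The window edit and the definition edit are both needed. The cost is SAP wording and programming, with no new data. Completers with no assessment after the first open-label dose will drop out of those denominators and have no end-of-treatment value, and Visit 1 abnormalities will move to the separate line.
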